### **Intra-cluster correlations (ICCs)**

Intra-cluster correlations will be calculated pre- and post-test for both individuals (pupils and staff) and schools. ICCs will be reported for all models with 95% confidence intervals.

### **Presentation of outcomes**

Standardised mean difference will be used to calculate the effect size. Total variance will be used in the calculation of the effect size, to account for the nested structure of the data.

The exact specification of the numerator and denominator is detailed below:

- Numerator = Adjusted mean difference estimate at each time point from the primary intervention effect analysis described above
- Denominator = Pooled unconditional variance for both intervention and control groups.

Bootstrapped confidence intervals will be used to reflect statistical uncertainty.

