## Sample size calculations overview

		Protocol	Randomisation
Minimum Detectable Effect Size (MDES)		Standardised mean difference = 0.15	Standardised mean difference = 0.17
Pre-test/ post-test correlations	level 1 (participant)	-	-
	level 2 (cluster)	-	-
Intracluster correlations (ICCs)	level 1 (participant)	0.03	0.041
	level 3 (cluster)	-	-
Alpha		0.05	0.05
Power		0.8	0.8
One-sided or two-sided?		Two-sided	Two-sided
Average cluster size		186 pupils 159 staff	220 pupils 26 staff
Number of clusters	intervention	29	31
	control	29	31
	total	58	62

		Protocol	Randomisation
Number of participants	intervention	4650 pupils 3975 staff	6429 pupils 724 staff
	control	4650 pupils 3975 staff	7194 pupils 896 staff
	total	9300 pupils 7950 staff	13623 pupils 1620 staff

The cluster sample size was determined a priori using a minimum detectable effect size (MDES) of 0.15 (standardised mean difference). The protocol presented different scenarios for sample size calculations based on a MDES between 0.10 and 0.20 (see Table 4 in the trial protocol). Presented in the table above is the sample size calculation for MDES of 0.15, which is in line with a projected school recruitment of 55 schools inflated to account for 15% attrition (58 in total). The estimate for the mean and SD of externalising difficulties in the control arm was based on the combined female and male scores from Elia et al. (2020). The intraclass correlation coefficient was assumed as 0.03. There is a lack of evidence on which to base assumptions for the pre-post correlation of externalising difficulties, so the sample size calculations were not adjusted to account for this. STATA was used for the power calculation using the following code: (MDE 0.15) power twomeans 5.21 4.76, sd(2.96) rho(0.03) m1(186) m2(186) power(0.8) cvcluster(0.5) cluster = 25 schools and 4,650 pupils per arm (increased to 29 schools per arm based on 15% school attrition).

The primary population of interest is pupils; estimates are also presented for staff. The pupil and staff sample sizes were determined from figures from three initial Local Authorities (LAs; Kent, Slough and Wiltshire). From this, 186 pupils per school were assumed after accounting for 35% study refusal and 25% attrition, resulting in an estimated sample size of 9300 pupils in total. 159 staff per schools were assumed after accounting for 35% study refusal and 25% attrition, resulting in 7950 staff in total.

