Pupils	Mean (SD)	Mean (SD)	
SDQ Externalising Symptoms	7.58 (4.24), n = 6429	7.52 (4.22), n = 7194	0.41
Year group (Cohort 2 only)	Count (%)	Count (%)	0.25
Year 8	2659 (41.4%)	2822 (39.2%)	
Year 9	2518 (39.2%)	2796 (38.9%)	
Missing	1252 (19.5%)	1576 (21.9%)	
Gender			<.001

	Intervention group (n = 31 schools)	Control group (n = 31 schools)	p
Female	3151 (49.0%)	3224 (44.8%)	(<.001)
Male	2978 (46.3%)	3668 (51.0%)	(<.001)
Non-binary	51 (0.8%)	64 (0.9%)	
Questioning	46 (0.7%)	52 (0.7%)	
Other	58 (0.9%)	59 (0.8%)	
Prefer not to say	145 (2.3%)	127 (1.8%)	
Ethnicity			0.13
Asian/Asian British	1492 (23.2%)	1753 (24.4%)	
Black/African/ Caribbean/Black British	398 (6.2%)	426 (5.9%)	
Mixed/Multiple ethnic groups	267 (4.2%)	346 (4.8%)	
Other ethnic group	244 (3.8%)	270 (3.8%)	
White	3699 (57.5%)	4074 (56.6%)	
Prefer not to say	329 (5.1%)	325 (4.5%)	
Staff			
ARTIC-35 sub-scales	Mean (SD), n = 724	Mean (SD), n = 896	

	Intervention group	Control group	p
	(n = 31 schools)	(n = 31 schools)	
Underlying Causes	4.75 (0.76)	4.67 (0.77)	0.04
Response to Problem Behaviour	5.05 (0.82)	4.90 (0.86)	<0.01
On Job Behaviour (Empathy and Control)	5.22 (0.75)	5.14 (0.74)	0.02
Self-Efficacy at Work	5.30 (0.92)	5.25 (0.94)	0.21
Reactions to Work	5.06 (0.78)	4.96 (0.84)	0.02
Gender	Count (%)	Count (%)	0.36
Female	515 (71.1%)	610 (68.1%)	
Male	206 (28.5%)	280 (31.3%)	
Non-binary	0 (0%)	0 (0%)	
Questioning	1 (0.1%)	0 (0%)	
Other	0 (0%)	1 (0.1%)	
Prefer not to say	2 (0.3%)	5 (0.6%)	
Ethnicity			0.26
Asian/Asian British	120 (16.6%)	160 (17.9%)	
Black/African/Caribbean/Black British	24 (3.3%)	16 (1.8%)	

	Intervention group (n = 31 schools)	Control group (n = 31 schools)	p
Mixed/Multiple ethnic groups	13 (1.8%)	17 (1.9%)	
Other ethnic group	20 (2.8%)	15 (1.7%)	
White	539 (74.4%)	677 (75.6%)	
Prefer not to say	8 (1.1%)	11 (1.2%)	

Note: ARTIC-35 = Attitudes Related to Trauma-Informed Care-35, EHCP = Education, Health and Care Plan, FSM = free school meals, SEND = special education needs and disabilities, SDQ = Strengths and Difficulties Questionnaire.

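### The SAP's effect-size formula divides the adjusted mean difference by a variance, so as written it is not the standardised mean difference it names or the one behind the SAP's own MDES

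*SAP*

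**What the plan says.** The SAP section Presentation of outcomes makes four statements about the effect size:

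- The metric: "Standardised mean difference will be used to calculate the effect size".
- Which variance is meant: "Total variance will be used in the calculation of the effect size, to account for the nested structure of the data".
- The status of the formula: "The exact specification of the numerator and denominator is detailed below".
- The formula: "Numerator = Adjusted mean difference estimate at each time point from the primary intervention effect analysis described above" over "Denominator = Pooled unconditional variance for both intervention and control groups".

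Neither a square root nor a standard deviation is mentioned there, and no other section supplies one for the reported effect size. The section Sample size calculations overview uses the same term for the design effect, "Standardised mean difference = 0.15" at protocol stage and 0.17 at randomisation. Both are backed by Stata code with an SD of 2.96.

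**The concern.** The numerator is in scale points and the denominator in points squared. The quotient therefore changes with the scale of the instrument, which is what standardising is meant to prevent. The SAP would be using one name for two different quantities: an SD-based one in the power calculation and a variance-based one in reporting.

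What is at stake is the size and comparability of the reported effect sizes and their bootstrapped intervals. Each outcome would be rescaled by its own SD. Outcomes with an SD above 1 would look smaller than they are, and those with an SD below 1 larger. An analyst who codes the rule as written gets a figure that is not a standardised mean difference. One who silently takes the square root departs from a specification that calls itself exact.

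**Working it through.** **1. The SAP's own standardised differences** (Sample size calculations overview)

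Inputs: means 5.21 and 4.76 at protocol stage, 5.21 and 4.70 at randomisation; SD 2.96.

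- Difference over SD: (5.21 − 4.76)/2.96 = 0.45/2.96 = 0.152, and (5.21 − 4.70)/2.96 = 0.51/2.96 = 0.172. These match the stated 0.15 and 0.17.
- Difference over variance (2.96² = 8.76): 0.45/8.76 = 0.051 and 0.51/8.76 = 0.058. Neither matches.

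**2. Check that 2.96 is used as an SD in the stated sample sizes**

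Formulas:

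- Individually randomised n per arm = 2 × [SD × (z₀.₉₇₅ + z₀.₈₀)/difference]².
- Multiply by [1 + (m − 1) × ICC]/RE, where RE = 1 − CV² × L × (1 − L) and L = m × ICC/(m × ICC + 1 − ICC).

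Results:

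- Randomisation stage (m = 219.73, ICC 0.041, CV 0.366): n = 528.79 before clustering, then 5,333.03 pupils and 24.27 schools per arm. The SAP states 5,333.02 and 24.3. Dividing 24.27 by 0.85 and rounding up gives the stated 29 schools.
- Protocol stage (m = 186, ICC 0.03, CV 0.5): n = 679.20 before clustering, then 24.70 schools per arm. Rounded up this is 25 schools, and 25 × 186 = 4,650 pupils, as stated.

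The design side of the SAP is therefore on the SD scale throughout.

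**3. Pooled baseline variance of the primary outcome** (Table 1, Imbalance at baseline)

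Inputs, as mean (SD): intervention "7.58 (4.24), n = 6429"; control "7.52 (4.22), n = 7194".

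- Pooled variance = (6428 × 4.24² + 7193 × 4.22²)/13621 = 17.888.
- Pooled SD = √17.888 = 4.229.

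**4. Size of the discrepancy**

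For a difference d, the ratio of the SD-based to the literal value is (d/SD)/(d/SD²) = SD. For the primary outcome at the baseline SD this is 4.23.

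| True standardised difference | Difference in points (× 4.229) | Literal formula (÷ 17.888) |
|---|---|---|
| 0.15 | 0.634 | 0.035 |
| 0.17 | 0.719 | 0.040 |
| 0.20 | 0.846 | 0.047 |

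At the planning SD the ratio would be 2.96.

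**5. Staff ARTIC-35 subscales, if the same formula is used** (Table 1; n = 724 and 896)

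| Subscale | Pooled variance | Pooled SD | Overstatement (1/SD) |
|---|---|---|---|
| Underlying causes | 0.586 | 0.766 | 1.31 |
| Response to problem behaviour | 0.710 | 0.842 | 1.19 |
| Empathy and control | 0.554 | 0.744 | 1.34 |
| Self-efficacy at work | 0.867 | 0.931 | 1.07 |
| Reactions to work | 0.662 | 0.814 | 1.23 |

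**The case against.** The best defence is that the wording is shorthand. The section opens by naming a standardised mean difference. Its second sentence is there to choose total over within-cluster variance, and the SAP divides by an SD wherever it actually computes such a difference. On this view the authors simply left out the words for the square root, and a competent analyst would supply them. That is probably what was intended, so a literal miscalculation is a risk and not a forecast. It does not rescue the text: the formula is offered as exact, and a correct calculation has to depart from it.

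Four stronger readings are tempting, and the SAP does not support them.

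- *The trial's conclusions would be wrong.* Estimates and tests come from the mixed model in the Analysis section and do not use this denominator. The adjusted difference in points and its p-value stand either way.
- *The result will be judged against the MDES.* The SAP uses 0.15 and 0.17 for power, and 0.20 (Interim analyses and stopping rules) for the number of schools needed. It nowhere says the final effect size will be set against them. A reader might well make that comparison, but it is an inference.
- *Every outcome would be shrunk about fourfold.* The factor is each outcome's own SD. The stated numerator also refers to the primary analysis, so carrying the formula over to staff outcomes is itself an assumption.
- *The bootstrapped intervals ignore clustering.* The section does not describe the resampling scheme, so nothing shows this.

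**Conclusion.** The point holds as an error in a stated formula. The specified ratio is not a standardised mean difference, and it contradicts the SD-based effect sizes in the SAP's own sample size section.

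The size is conditional. The factor of about 4.2 for SDQ externalising requires literal application and a pooled unconditional SD at follow-up close to the baseline 4.23. The range of 1.07 to 1.34 in the other direction for ARTIC-35 requires that the same formula be used for staff outcomes, with SDs near those in Table 1. What would be affected is the reported effect size and its interval, and any comparison a reader makes with an SD-based benchmark.

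**What to change.** Replace the denominator line in Presentation of outcomes with: *Denominator = square root of the pooled unconditional total variance (pooled total SD, including all variance components: school, individual and residual) of both arms.*

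The residual needs to be named. The model has two follow-up occasions with random intercepts for individuals within schools, so a sum of school and individual components alone would leave out the occasion-level variance, make the SD too small and inflate the effect size.

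The cost is one line of SAP wording. It needs no new data and changes neither the design nor the model.
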